## **9. Data collection**

After follow-up, data will be extracted from NPR with regards to diagnosis codes of vascular events, bleeding episodes, LOS and death. In case of events, the patient's medical charts will be requested and evaluated. The study is approved by the Danish Data Protection Agency.

## **10. Authors**

According to alphabetical order, however, with writer as primary author and [name] as senior author. (13.1)

## **11. Study committees**

The LCFHK will lead the logistic coordination of the different study committees.

### **11.2 Clinical events committee**

A clinical events committee will be founded, consisting of the writer and [name], where uncertainties regarding verification of diagnosis will be discussed. (Appendices 2+3)

## **12. Ethics and Legal aspects**

### **12.1 Ethic Committee (EC)**

The study will be presented to the Scientific Ethics Committee (SEC) and receive approval from here. It has been preliminarily approved as a quality-control study, as Hvidovre, Hørsholm and Farsø amongst others presently use this treatment as standard of care.

### **13. Ethical aspects and perspectives of the study**

The duration of thrombosis prophylaxis after THA and TKA is subject to debate, both nationally and internationally. The degree of thrombo prophylactic effect vs. discomfort for the patient, bleeding-related side effects and, not the least, health related expenses need to be investigated in the “real life” setup in which the patients are operated. In Denmark the Danish Society of Orthopedic Surgeons recommend 7 days of treatment as a compromise (international recommendations up to 35 days), but also allow prolonged treatment on indication (unspecified). Studies suggest that with early mobilization and an uncomplicated postoperative phase the risk of VTE is significantly decreased. Thus there is no indication of prolonged thrombosis prophylaxis with related increased risk of bleeding-related side effects in this group(16). This study with short treatment thrombosis prophylaxis in patients having THA/TKA in a fast-track setup is in accordance with highest international expertise(17). Additionally there is disagreement regarding the American guidelines, where patients receive treatment with acetylsalicylic acid only(9).

We believe that this is a very important study, as it can influence, not only orthopedic recommendations, but generally on major surgery, such as abdominal surgery, gynecology, and other major surgical specialties using a fast-track setup(26;27). We believe that literature and, not in the least clinical experience, provide the background for a study of this character. Empirically, more and more surgeons do not follow the international recommendations and create their own. The Danish Society of Orthopedic Surgeons recommend 7 days of postoperative thrombosis prophylaxis (different from international recommendations), proving the lack of agreement in this area.

The design of the study will ensure that all data and the analysis of data will be in accordance with the Helsinki Declaration as well as local laws and regulations. The investigators will at any point allow the Steering committee or representatives of the Steering committee to review documents in order to ensure this.

### Bleeding

The safety endpoint is the frequency of bleeding(28)observe red no later than 2 days after last administration of thrombosis prophylaxis. Bleeding more than 2 days after last dose of thrombosis prophylaxis will not be considered as a side-effect.

#### **Diagnosis of bleeding**

In case of bleeding all information, ie. Anesthesia-charts, laboratory results, ultrasound findings, must be registered in the medical chart. All bleeding-episodes will be classified according to predefined criteria:

Serious bleeding

Minor bleedings

#### **Serious Bleedings are:**

- Fatal bleeding
- Bleeding in a critical organ(retroperitoneal, intracranial, intraocular, intraspinal, pericardiac bleeding with tamponade, intramuscular bleeding with compartment syndrome)
- Bleeding needing surgical intervention (including joint puncture and aspiration)
- Bleeding leading to infusion of >1 portion of SAGM/full blood
- Bleeding index  $\geq 2$  (defined as number of transfused portions of erythrocytes + diff between hemoglobin before and after bleeding measured in gram/dl).
- Drop in hemoglobin of > 30g/L (=1,9mmol/L)
- **All bleedings not classified as serious bleedings will be classified as minor bleedings**

## 17. Appendix 3

Definition of clinical outcomes:

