#### Observations and tests

#### 3.2 Plan:

#### Day -7 til -1:

The patient goes through physical examination and demographics are registered (appendix 4).

**Dag 0:** defined as day of surgery

Patient has surgery

Thrombosis prophylaxis according to local guidelines (appendix 1).

**Dag 3 ± 2:** Patient is discharged (4.3) and ceases thrombosis prophylaxis.

**Dag 90 ± 5:** End follow-up

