## 17.5 Other thromboembolic events

Need to be defined by a relevant specialist.

## 18. Appendix 4

Date of surgery

Social security number

Joint (knee/hip)

Height: \_\_\_\_\_ cm

Weight: \_\_\_\_\_ kg

Hemoglobin level \_\_\_\_\_ mmol/l

(Taken no more than 1 week previously)

Patients' blood type?

Living conditions (alone, with spouse/others, in institution (nursing home etc.))

Smoking (yes/no)

Alcohol >2 units a day (yes/no)

Do you use walking aids prior to admission?

Are you feeling well rested in the morning?

Do you snore loudly?

Do you use compressive stockings regularly?

Do you receive treatment for high cholesterol (yes/no)

Do you receive treatment for high blood pressure (yes/no)

Do you have Type 1 diabetes (yes/no)

Do you have Type 2 diabetes (yes/no)

Have you had a previous cerebral attack?

Have you had a previous venous thromboembolic event?

Do you receive medication for any type of heart disease?

Do you receive medication for any type of pulmonary disease?

Do you receive medication for any type of psychiatric disease?

Do you have a family member who has had a deep venous thrombosis or pulmonary embolus?

Do you have a contraindication for antithrombotic medication?

Do you use antithrombotic medication regularly (marevan, acetyl salicylic acid etc)?

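### Does the bleeding index in Appendix 2 undercut the 30 g/L haemoglobin line and leave the serious/minor split undefined?

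*Combined protocol and SAP*

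**What the plan says.** Section 6 announces a safety analysis of bleeding and refers to Appendix 2 (section 16). That appendix states: "The safety endpoint is the frequency of bleeding", limited to bleeds seen within 2 days of the last prophylaxis dose. It adds that "All bleeding-episodes will be classified according to predefined criteria", with two classes, serious and minor.

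The serious list has six items: fatal bleeding, bleeding in a critical organ, bleeding needing surgical intervention, and three that use transfusion or haemoglobin:

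- the transfusion line: "Bleeding leading to infusion of >1 portion of SAGM/full blood";
- the index line, met at a value of at least 2, where the index is "defined as number of transfused portions of erythrocytes + diff between hemoglobin before and after bleeding measured in gram/dl";
- the separate line for haemoglobin alone, which reads "Drop in hemoglobin of > 30g/L (=1,9mmol/L").

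Every bleed not on the list is minor. The list does not say which blood samples supply the before and after values.

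The only haemoglobin field on a form is in Appendix 4 (section 18). It is preoperative, in mmol/l, "Taken no more than 1 week previously". Section 3.2 places that form at day -7 to -1.

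**The concern.** The list seems to hold two haemoglobin thresholds for the same untransfused bleed: 20 g/L through the index and 30 g/L on its own line. The lower one decides, so anyone who takes 30 g/L as the haemoglobin criterion would misread a reported serious-bleeding rate.

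The definition also looks incomplete in four ways. It does not state that one item is enough. It does not say whether the haemoglobin difference is a fall, a rise or an absolute value. It mixes g/dL, g/L and mmol/L. It does not name the before sample: after arthroplasty, a preoperative value and the last value before the bleed may differ, and that could change the class.

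At stake is the reproducibility of the serious/minor split within the safety analysis.

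**Working it through.** **Inputs** (all from Appendix 2 unless marked). Index threshold: at least 2. Index = portions + haemoglobin difference in g/dL. Drop line: more than 30 g/L, equated with 1.9 mmol/L. Transfusion line: more than 1 portion. Conversion: 1 g/dL = 10 g/L.

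**The plan's own figure.** The documents give no molar mass for haemoglobin. Assuming 16.114 g/mmol, 30 / 16.114 = 1.86 mmol/L. Over an assumed range of 16.0 to 16.2 the result runs from 1.88 to 1.85. All of these round to 1.9, so the stated equivalence holds.

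**Where the index bites.** With the difference taken as before minus after, index = portions + fall/10 (fall in g/L).

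| Portions | Fall needed for index of at least 2 |
|---|---|
| 0 | (2 - 0) × 10 = 20 g/L |
| 1 | (2 - 1) × 10 = 10 g/L |
| 2 | (2 - 2) × 10 = 0 g/L |

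A fall above 30 g/L gives an index above 30/10 = 3 before any portion is added. No such case escapes the index, so the drop line adds none. Untransfused falls of 20 to 30 g/L inclusive are serious by the index alone.

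**Does the overlap misclassify?** No. Every bleed still receives exactly one class. The overlap also requires both lines to use the same pair of values. Suppose instead that the drop line ran from the preoperative value, the index ran from the last value before the bleed, and the operation had lowered haemoglobin by an assumed 20 g/L. A further fall of more than 30 - 20 = 10 g/L but less than 20 g/L would then meet the drop line and not the index.

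**One item or all?** Requiring all six would mean that every serious bleed is fatal, in a critical organ and operated on. That reading is untenable.

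**Sign.** Read as after minus before, the index could not be met by any fall with 0 or 1 portion, which defeats its purpose. Read as an absolute value, the class changes only for a net rise of at least 10 g/L with 1 portion or at least 20 g/L with none. The order of before and after, and the word for a fall on the next line, settle the meaning.

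**Units.** Entering mmol/L unconverted would move the untransfused threshold to 2 × 30/1.9 = 31.6 g/L. That would contradict the index line, which names g/dL. It would be a data error, not a gap in the definition.

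**Baseline.** If the preoperative value were used and the operation had lowered haemoglobin by 0, 10 or 20 g/L (an assumed range), the further fall needed without transfusion would be 20, 10 or 0 g/L. The index line, however, ties both values to the bleed. Section 1.1 cites Appendix 4 for risk factors, and nothing makes its preoperative field the source for the index.

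**The transfusion line.** It is not redundant. It decides a two-portion bleed with a net haemoglobin rise or a missing haemoglobin and, read literally, a transfusion of full blood, because the index counts erythrocyte portions only.

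**The case for a change.** The best argument for a change is that the criteria are promised in advance, yet two assessors with the same chart could choose different before values and so assign different classes. A committee is not a written rule. Naming the samples would take a few lines, and a table of serious bleeds by qualifying criterion would show how many rest on the index alone. Section 8 also lets the committee recommend early termination for an unacceptable safety profile, so the classification could carry some weight.

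Part of this stands: the exact samples are not named, and nothing says that the two haemoglobin lines share them. But the plan supplies the means to resolve it. Appendix 2 requires laboratory results to be in the chart. Section 9 has charts requested and evaluated when events occur, and section 19, item 11 extends review to all readmissions within 90 days. Section 11.2 gives a clinical events committee the task of settling uncertain diagnoses and refers to Appendix 2. Section 8 sets no numerical limit on serious bleeding, and section 4 attaches no test or power to it. The extra table would add reporting without correcting a result.

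**Conclusion.** No change is needed. The arithmetic is right: given one pair of haemoglobin values for both lines and a difference that means a fall, the index is met at 20 g/L without transfusion and at 10 g/L with one portion, and the 30 g/L line decides nothing. That is an overlap within an any-one-of list, not a contradiction that produces a wrong class. This review takes no view on which threshold is preferable.

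The questions of one item or all, sign and units disappear on a plain reading. What is left is a detail of sample selection that assessors with the chart can settle sensibly. It can affect only bleeds whose class turns on a haemoglobin line. Fatal, critical-organ, surgical and more-than-one-portion bleeds stay serious whatever sample is chosen. Overall bleeding frequency, the hypothesis and the sample size are unchanged. How many bleeds might change class cannot be computed from the documents, and the 0 to 20 g/L range for operative loss is an assumption.

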### 17.1 DVT

Diagnosis done by ultrasound (if not possible venography). The main criteria for DVT is a negative compression test with ultrasound(9).

### 17.2 Pulmonary embolism

Diagnosed by

- Spiral CT-scan (29)
- Perfusion-ventilation scintigraphy(9)
- Pathological removal of embolus(9)

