## **Background:**

Surgery is recognized as being related to the development of thrombosis, especially after major orthopedic surgery (1;2). These complications are defined as venous thromboembolic events (VTE), including deep venous thrombosis (DVT) and pulmonary embolism (PE).

Pharmacological prophylaxis reduces the risk of thrombosis and recommendations (grade 1a) from the American College of Chest Physicians (ACCP) are one of three following anticoagulantia:

1: Low molecular weight heparin (LMWH)

2: Faktor Xa-inhibitors

3: Vitamin-K-antagonists

Recommended duration of thrombosis prophylaxis is 10 days after total knee arthroplasty (TKA) and 35 days after total hip arthroplasty (THA) (3).

In the United States of America most surgeons follow ACCP guidelines. Studies have shown that about 90 % of surgeons adhere to guidelines, however, many use additional prophylaxis such as compressive stockings(4). More recent investigations find a lower compliance amongst surgeons world wide of about 50% (5). There are disagreements about the validity of the before mentioned guidelines due to the many exclusion and inclusion criteria in the analyzed studies and due to the fact that it is the thoracic surgeons who dictate the orthopedic surgeons guidelines(6), therefore the American Academy of Orthopedic Surgeons (AAOS) has developed their own guidelines. The main difference between ACCP and AAOS guidelines is the use of compressive stocking and acetylsalicylic acid as only prophylaxis in patients at risk of bleeding and a general disagreement on the relationship of DVT and PE(7).

In Denmark, the Danish Society of Orthopedic Surgeons (DSOS) has their own guidelines of 7 days of postoperative thrombosis prophylaxis which illustrates the controversies in this area.

The few studies who do not comply with ACCP guidelines, using acetylsalicylic acid (and early mobilization) as only prophylaxis show very low frequencies of vascular events (8-11), raising doubts about the best choice of treatment, especially considering increased mortality with LMWH compared to acetylsalicylic acid(12).

Preliminary uncontrolled studies in TKA have shown that early mobilization (<24 hours after surgery) reduces risk of postoperative VTE in patients treated with LMWH(13), and as frequency of DVT following TKA is decreasing over time using warfarin (VKA) as prophylaxis(14), interest in postoperative mobilization is increasing.

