The trend towards enhanced recovery protocols (fast-track surgery) where optimized pain treatment, early mobilization (<24 hours), preoperative patient information etc. aims to decrease length of hospital stay. Data on THA and TKA patients from Hvidovre Hospital proves that 92 % of patients were discharged within 5 days and 41 % within 3days(15).

An un-published preliminary study from Hvidovre Hospital in about 2000 patients shows very low frequency of symptomatic VTE in 90-days follow-up, with mortality of 0.15%, DVT/PE/death in TKA of 0.66%

and 0.52% in THA when using a fast-track setup (16). This is lower than comparable literature with thrombosis prophylaxis for 35 days postoperatively.

A group of experts has suggested that pharmacological thrombosis prophylaxis in patients with early mobilization is non-obligatory, this would result in decreased side-effects such as bleedings, less inconvenience in the patients and economical advantages(17). This has resulted in short prophylaxis treatment being standard of care in several departments in Denmark (i.e. Hørsholm, Hvidovre and Farsø hospitals).

No previous study has been published with a detailed description on the risk of vascular events, including arterial complications, using short-treatment thrombosis prophylaxis in a fast-track setup after THA/TKA or commented on identification of risk factors(2;18;19).

It must be mentioned that Asian patients (Korea, China etc.) do not have a tradition for thrombosis prophylaxis after THA due to the low frequencies of VTE without prophylaxis. In this context, differences in genetics and dietary habits etc. must be considered (20;21).

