## **1. Intention of study**

### **1.1 Primary outcome**

To conduct a high quality cohort study to investigate the frequency of symptomatic DVT, PE, acute myocardial infarction (AMI), stroke and other vascular events and/or death of other causes in patients having elective uni and bilateral THA/TKA, revision THA/TKA and uni-KA in a fast-track setup including short treatment thrombosis prophylaxis( $3 \pm 2$  days). Additionally, identification of risk factors for such events will be attempted (Appendix 4).

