### **Cardiovascular death**

Death of vascular causes include cardiovascular, cerebrovascular and death of other vascular causes or death with no clear documentation of non-vascular cause. Ex:

Vascular death: Sudden death, MI, unstable angina pectoris, other CAD, stroke, arterial embolism, pulmonary embolism, dissecting aorta, heart insufficiency, cardiac arrhythmia, or death from bleeding (non-trauma related)

Non-vascular death: Respiratory failure, pneumonia, cancer, trauma, suicide or other defined cause (i.e. liver or renal failure)

Death of unknown /uncertain causes will be categorized as vascular death.

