## 19. Protocol editing and changes after study initiation

- 1) **Project leader and coordinating investigator:** Changed from [name] to [name]
- 2) **Other investigators:** The following investigators have been removed as the study was not initiated at their institutions: [name] MD, Århus Universitety Hospital, THG Århus, [name] MD, Regionshospitalet Silkeborg.  
The following investigators have been edited: [name] MD, Gentofte Hospital Gentofte.  
The following investigators have been added: [name] MD, Sydvestjysk Sygehus Grindsted/Esbjerg
- 3) **Statistician:** [name] is no longer responsible for statistics. [name] has been added and additional assistance will be acquired as needed.
- 4) **Study sites:** The following study sites have not participated: Regionshospitalet Silkeborg, Hørsholm Hospital (due to closure). The following study sites have been added: Sydvestjysk Hospital Grindsted/Esbjerg April 2010, Gentofte Hospital, November 2012.
- 5) **Background:** Hørsholm Hospital has been mentioned as having used short-treatment prophylaxis as standard of care. This is a mistake and should be omitted.
- 6) **2.1 Design:** Due to a large number of available patients, it has been decided to expand the study size. The intention is now to include 5000 PRIMARY operations in addition to a number of revisions and uni-KA. 3.
- 7) **3. Patient selection:** Changes according to 4) **Study sites.**
- 8) **3.3 Discharge criteria:** Thrombosis prophylaxis in patients with LOS >5 days: DOS guidelines are not 7 days, but 5-10 days in TKA and 7-35 days after THA.
- 9) **4. Statistics:** The exact number of patients when using a Two-tailed one sample difference from constant test with the in the protocol mentioned specifications is 2838. Using the same test, 2076 patients will be needed to detect a 1% increase in frequency of symptomatic VTE, using  $\alpha$ : 0.05,  $\beta$ : 82 and a baseline risk of 1% with 35 days of treatment with LMWH.
- 10) **7. Duration of study:** As the database of this study forms the core of several independent studies on co-morbidity, duration of this study has been extended, and database registration is expected to last until ultimo 2016

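### The symptomatic VTE rate omits any fatal PE that presents as a sudden or unexplained death without imaging or pathology; the primary composite does not.

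*Combined protocol and SAP*

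**What the plan says.** The Background section gives the only definition of VTE: "These complications are defined as venous thromboembolic events (VTE), including deep venous thrombosis (DVT) and pulmonary embolism (PE"). Death is not part of it.

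Section 17.2 lists three ways to establish PE: spiral CT, perfusion-ventilation scintigraphy, and "Pathological removal of embolus(9"). It has no category for fatal, probable or non-excludable PE.

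The definition of cardiovascular death in Appendix 3 lists sudden death and PE as separate items: "Vascular death: Sudden death, MI, unstable angina pectoris, other CAD, stroke, arterial embolism, pulmonary embolism, dissecting aorta". It then adds: "Death of unknown /uncertain causes will be categorized as vascular death".

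Hypothesis 1.2 is that symptomatic thromboembolic events are not more frequent under short prophylaxis. Item 9 of Section 19 gives symptomatic VTE its own calculation: "Using the same test, 2076 patients will be needed to detect a 1% increase in frequency of symptomatic VTE". The baseline there is 1% under 35 days of LMWH, with no source or outcome definition.

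The primary outcome in Section 1.1 is wider. After DVT, PE, AMI and stroke it adds "other vascular events and/or death of other causes in patients having elective uni and bilateral THA/TKA".

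**The concern.** Consider a patient who is discharged, stops prophylaxis and dies suddenly at home, with no scan and no autopsy. On the written definitions this is a vascular death and not a PE, so it never enters the symptomatic VTE rate. Yet fatal PE is the gravest thing that shortening prophylaxis could cause, and a death at home is where imaging is least likely. In a single-arm study whose hypothesis is no increase, undercounting leans towards the favourable answer.

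The plan is cautious elsewhere, since deaths of unclear cause go to the vascular side. That caution stops short of the VTE rate. At stake is how much a statement of no increase in VTE can claim.

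**Working it through.** **1. Inputs**
- VTE baseline 1%, increase of 1 point, two-sided one-sample test, alpha 0.05, power 82%, n = 2076 (Section 19, item 9, with Section 4).
- Planned size: 5000 primary operations (Section 19, item 6).
- 90-day mortality 0.15% in a preliminary series of about 2000 patients (Background).
- Assumption: the share of patients with a fatal PE not counted as VTE, m, lies between 0 and 0.15 points. The top of the range treats every death at the preliminary mortality as an uncounted PE, so it is a ceiling and not an estimate.

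**2. The plan's own figures.** An exact two-sided binomial test with equal tails, taking the smallest n with power of at least 82%:
- 4% (null) against 3%: n = 2838, as item 9 states.
- 1% (null) against 2%: n = 1143, not 2076.
- 3% (null) against 2%: n = 2076.

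The VTE figure therefore does not follow from the rates given for it. That is a separate matter. Below, 2076 is used simply as a stated sample size.

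**3. Deaths involved.** 0.0015 × 5000 = 7.5, and 0.0015 × 2076 = 3.1.

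**4. Effect on the rate.** Observed rate = true rate − m. At the ceiling, 2.0% becomes 1.85% and 1.5% becomes 1.35%.

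**5. Effect on power to show an excess over 1%.** Let c be the smallest count with P(X ≥ c | n, 0.01) ≤ 0.025. This gives c = 31 at n = 2076 and c = 65 at n = 5000. Power is P(X ≥ c | n, true rate − m).

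| True VTE | m (points) | n = 2076 | n = 5000 |
|---|---|---|---|
| 2.0% | 0 | 96.3% | 99.99% |
| 2.0% | 0.15 | 90.5% | 99.9% |
| 1.5% | 0 | 53.4% | 89.1% |
| 1.5% | 0.05 | 46% | 83% |
| 1.5% | 0.10 | 38% | 74% |
| 1.5% | 0.15 | 31.0% | 63.7% |

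**6. Does it move an upper confidence limit across 1%?** Subtracting mortality from the preliminary DVT/PE/death rates gives 0.66 − 0.15 = 0.51% (TKA) and 0.52 − 0.15 = 0.37% (THA). This assumes equal mortality in both joints and no overlap of deaths with DVT/PE. In 5000 patients that is 25.5 and 18.5 events. Adding all 7.5 deaths gives 33 and 26. The exact 95.2% upper limits are 0.93% and 0.76%, both below 1%. To cross 1% one must start higher: 30 events has an upper limit of 0.86%, 36 events 0.998% and 38 events 1.04%.

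**The case against.** Four points can be made for the plan.

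**The deaths are not lost.** The primary composite includes death, and the interim looks against 4% in Section 8 use the same maximum rate as the main calculation in Section 4. This stands. A reader might infer that the study departs from its preliminary series, which reported "with mortality of 0.15%, DVT/PE/death in TKA of 0.66"%. It does not: the primary outcome also combines VTE with death.

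**Bias against the 1% baseline is not shown.** A reader might infer that the comparison is tilted towards no increase. That requires the baseline to have counted unexplained deaths, and item 9 does not say. If the baseline used confirmed events only, the loss is largely shared. Resting the conclusion solely on a rate that adds the deaths would then create the opposite bias. This stands.

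**No decision rule is crossed.** It is tempting to say that a handful of deaths would push the upper limit past 1%. The plan sets no such rule for VTE, the 95.2% interval belongs to the final analysis against 4%, and on the preliminary rates the limit stays below 1% (step 6). This stands.

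**The exclusion is not absolute.** Pathological removal may be meant to cover an embolus found at post-mortem, and the clinical events committee (Section 11.2) discusses uncertain diagnoses. This stands in part. It does not help a death without autopsy, no written rule tells the committee how to assign such a death, and in a single-arm study everyone knows that short treatment was intended.

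Requiring objective confirmation of PE is a defensible choice for specificity. It still leaves open what the VTE rate does with deaths that could not be confirmed.

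**Conclusion.** The point holds for the symptomatic VTE rate itself. Followed as written, the plan leaves out any fatal PE that has neither imaging nor pathology, so that rate is too low to the extent that such deaths were PE.

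The understatement is at most about 0.15 points if the preliminary mortality applies. That mortality rests on roughly 0.0015 × 2000 = 3 deaths, and a higher mortality in this cohort would raise the ceiling. At the ceiling, the loss of power matters for a true VTE rate near 1.5% and is small at 2%, the rate that item 9 sets out to detect.

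The documents do not support saying that the comparison with 1% is biased, because the baseline's definition is not given. Nor do they support any effect on the primary composite or the 4% threshold. This is a worthwhile and inexpensive clarification, not a flaw in the main analysis.

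**What to change.** In Appendix 3:
- State that PE proven at autopsy counts as PE.
- Define VTE-related death as death from PE, or sudden or unexplained death in which PE cannot be excluded.

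In the analysis:
- Report the 90-day symptomatic VTE rate with an exact confidence interval twice, without and with VTE-related deaths.
- In item 9, give the source of the 1% baseline and say how it counted fatal and suspected PE. Make the comparison with the version that matches.
- Claim no increase only if it holds under both versions, or disclose the difference.

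The cost is one definition and one extra results line. Section 9 already extracts deaths from the NPR and requests charts in case of events. The downside is a possibly higher, more cautious VTE rate.
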